Restorative approach procedures. The study OT will deliver the restorative approach starting at the 3rd visit. The selected self-care tasks include any in-home activities that the patient does to take care of self and others, which are not limited to basic ADL. In the beginning of each visit, the study OT and the patient together identify 2 or 3 activities where the patient has experienced limitations or difficulties. The study OT will apply one or two activity grading principles to each selected activity. The intervention intensity will be kept at the moderate level (somewhat hard) using the Omni Scale, which is a rated perceived exertion scale. For example, if a patient experiences difficulty to returning pantry items to overhead shelves, the study OT can let the patient wear a weighted wrist cuff while sorting pantry items (increase the load), restore items to an overhead versus shoulder-high shelf (increase the movement distance), restore items into different locations on the shelves (change of movement direction), speed up while storing items (increase the movement speed), store 10 pantry items versus store five items at a time (increase the endurance), or carry groceries with a shopping bag and store pantry items from the groceries to the overhead shelves (increase the activity complexity by combining two tasks, carrying groceries and sorting the pantry items after shopping). Patients will practice each selected task for 15 to 20 minutes with a rest break if needed.

Allowed interventions. All participants will receive the care plan approved by their home health agency. The care plan should include regular home health rehabilitation therapy.

Adherence Assessment. The adherence for the ADL-enhance intervention will be evaluated by the number of sessions that the patient is able to complete within the study period (60 days).

Study Procedures.

[figure not shown]
6.1. Schedule of Evaluations.

	Baseline	Post-intervention (Post intervention \pm 7 Business days) ⁺	One-month follow-up (Day 30 post intervention \pm 7 Business days)	3-month follow-up (Day 90 post intervention \pm 7 Business days)
Assessment of Motor and Process Skills	x	x	x	
Activity Measure for Post-Acute Care Home Health Short Form	x	x	x	x
OASIS self-care items from chart review	x	x		
Box and Block Test	x	x	x	
Jebesen Hand Function Test	x	x	x	
Timed-Up-and-Go Test	x	x	x	
Short Physical Performance Battery	x	x	x	
PEG three-item scale	x			
Patient Health Questionnaire-9	x			

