Saint Louis University Mental Status Exam	x			

Patient demographic background and medical info from self-report as well as chart review	x			
Patient satisfaction survey		x		
Adverse events (hospitalization, falls, emergency room visits)		x	x	x

+: The end of ADL-enhanced program, the last home visit of usual care, or 6 weeks from the baseline assessment, which occurs last.

Study visit schedule.

Description of Evaluations.

Screening evaluation.

The screening will occur over the phone within three business days after a home health care provider has mentioned the study opportunity to the patient and received verbal permission from the patient for the research coordinator to contact him/her. The research coordinator will follow a phone script approved by the UF IRB for this phone screening. The coordinator will obtain a verbal permission prior to proceeding with screening questions from the potential research participant after a brief introduction of the study. These screening questions are:

1. Are you aged 65 years or above?
2. How many medical conditions, including chronic conditions, that you currently have? Examples of the conditions include but not limit to diabetes, heart disease, high blood pressure, joint disease or arthritis, and lung disease.
3. Do you have any of the following conditions?
 - an elective joint replacement surgery in the last month
 - orthopedic or heart surgery in the last month
 - lower extremity amputation
 - currently receiving treatment for cancer
 - an ongoing dialysis treatment
 - a neurologic condition, such as stroke or Parkinson's disease, that significantly limits your movements
 - congestive heart failure that is at the terminal stage

In addition to these questions, the interviewer will administer the "Six-item cognitive screener" to determine the potential participant's cognitive ability. If a participant scores a 4, 5, or 6 on the screener, they will be eligible for the study.

Enrollment, baseline, and randomization.

Enrollment. A patient is considered enrolled in this study when he or she meets the eligibility criteria and signs the informed consent form.

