Randomization. Randomization will occur after the baseline assessment. [name] (Co-I) will generate a randomization list using a computer software and seal the list in opaque envelopes. The on-site research coordinator will open one envelope after a patient has completed the baseline assessments. If the patient is assigned to the ADL-enhanced group, the coordinator will notify the study OT to start intervention.

Post-intervention evaluation.

The satisfaction survey will be given to the patient in the experimental group after the last visit of ADL-enhanced intervention by the research coordinator over the phone.

For the group that will receive the ADL-enhanced program, the post-intervention evaluation conducted by the blinded outcome assessor will occur within seven business days after the completion of the last visit of usual home health rehabilitation therapy or ADL-enhanced intervention, whichever occurs last. For the control group, the post-intervention evaluation conducted by the blinded outcome assessor will occur either 6 weeks after the baseline assessment or after the last usual home health visit, whichever occurs last. Patients will be instructed not to discuss their therapy content with the blinded outcome assessor and vice versa. The following assessments will be administered during the post-intervention evaluation visit.

1. Assessment of Motor and Process Skills
2. Activity Measure of Post-Acute Care Home Health Short Form
3. Jebsen Hand Function Test
4. Box and Block Test
5. Timed-Up-and Go
6. Short Physical Performance Battery
7. Adverse events questionnaire

The research coordinator will extract the patient's OASIS self-care item scores (scores at the start of care and discharge) from medical chart when the patient has been discharged from home health care or 60 days after admission.

One-month follow-up evaluation.

The one-month follow-up evaluation conducted by the blinded outcome assessor will occur within seven business days one month after the completion of the last visit of usual home health rehabilitation therapy or ADL-enhanced intervention (Day 30 post intervention), whichever occurs the last. Patients will be instructed not to discuss their therapy content with the blinded outcome assessor and vice versa. The following assessments will be administered during the one-month follow-up evaluation visit.

1. Assessment of Motor and Process Skills
2. Activity Measure of Post-Acute Care Home Health Short Form

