3. Jebsen Hand Function Test
4. Box and Block Test
5. Timed-Up-and Go
6. Short Physical Performance Battery
7. Adverse events questionnaire

Final evaluation or three-month follow-up evaluation.

The final evaluation will occur over the phone by the research assistant or coordinator within seven days three months after the completion of the last visit of usual home health rehabilitation therapy or ADL-enhanced intervention (Day 90 post intervention). The following assessments will be administered during the final evaluation.

1. Activity Measure of Post-Acute Care Home Health Short Form
2. Adverse events questionnaire

Data analysis plan.

Preliminary analysis. We will compare participant demographics and covariates (e.g., pain levels) between the two groups. Variables with statistically significant differences will be included in the subsequent statistical models as covariates. We will graph spaghetti plots for repeated measurements and examine for outliers.

Data analysis. Since ADL and physical functioning outcomes will be collected over three time points (baseline, post-treatment, one-month follow-up), the mixed-effects linear regression modeling will be conducted to fit the data, in which a random-effects term is included to accommodate within-subject data correlation and a quadratic growth curve is included to describe the temporal trend of the response.

For **Aim 1**, which will estimate the preliminary effect of the ADL-enhanced program on improving ADL, three separate mixed-effects regression analyses will be conducted for the Motor Skills scores of the Assessment of Motor and Process Skills (the primary outcome), the Activity Measure of Post-Acute Care Home Health Short Form, and the OASIS self-care items, in each of which sex, race, age, and other covariates will be included in the model.

For **Aim 2**, which will estimate the preliminary effect of the ADL-enhanced program on physical functioning of the upper extremity and lower extremity, four similar separate analyses will be conducted for the Box and Block Test, Jebsen Hand Function Test, Timed-Up-and Go, and Short Physical Performance Battery.

For **Aim 3**, the program completion rate and satisfaction rate will be compared to the benchmark, 75%. Fisher's Exact Test will be performed to compare the proportion of patients who experience adverse events of hospitalization, emergency room visits, or falls (adverse event rate) between the two groups.

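### When therapy ends before week 6, the schedule table and the text date follow-up from different points; separately, two visit windows disagree for all patients

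*Combined protocol and SAP*

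**What the plan says.** **Table.** The footnote to section 6.1, Schedule of Evaluations, defines the post-intervention time point as "The end of ADL-enhanced program, the last home visit of usual care, or 6 weeks from the baseline assessment, which occurs last". It makes no distinction between arms. The later columns are headed "One-month follow-up (Day 30 post intervention" and "3-month follow-up (Day 90 post intervention". All three columns carry a tolerance of plus or minus 7 business days.

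**Post-intervention evaluation (text).** The experimental visit is to take place "within seven business days after the completion of the last visit of usual home health rehabilitation therapy or ADL-enhanced intervention, whichever occurs last". This has no 6-week floor, and the window runs forward only. The control visit "will occur either 6 weeks after the baseline assessment or after the last usual home health visit, whichever occurs last". This has the floor, but no window width.

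**One-month follow-up evaluation (text).** In both arms the visit falls "one month after the completion of the last visit of usual home health rehabilitation therapy or ADL-enhanced intervention (Day 30 post intervention", taking the later of the two. There is no 6-week floor, yet the label is the one used in the table.

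**Final evaluation (text).** The contact falls "three months after the completion of the last visit of usual home health rehabilitation therapy or ADL-enhanced intervention (Day 90 post intervention", again without a floor. Its tolerance is given in days, not business days: it "will occur over the phone by the research assistant or coordinator within seven days three months after the completion".

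**Data analysis plan.** The mixed model uses three time points and a quadratic growth curve, without saying whether time is nominal or actual. The proportions of patients with adverse events are compared by Fisher's exact test.

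**The concern.** The primary hypothesis is about less decline at follow-up after treatment completion, so the interval between the post-intervention and follow-up visits is part of what is being estimated. If the rule for that interval differs between arms, the contrast mixes treatment effect with elapsed time.

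The two readings pull in opposite directions. If staff follow the text, controls who finish usual care early have less time in which to decline, and less time for an adverse event to occur before each contact. That tends to count against the programme. If staff use the footnote date for all visits, the same controls have been off therapy longer when they are assessed, which can favour the programme. Nothing in the plan tells staff which to follow, and the analysis section does not say that actual dates will be used to absorb the difference.

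**Working it through.** **Inputs.** Baseline is day 0. Six weeks is 42 days (footnote and control text). Follow-up offsets are 30 and 90 days (table headings and text). L is the day of the last therapy visit of either kind. The documents give no figure for L in either arm, so the values below are assumptions that show the range. The plan states no interval of its own to reproduce.

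**Footnote date used for all visits, both arms.** A = max(L, 42); post = A; one-month = A + 30; three-month = A + 90. The post to one-month interval is always 30 days.

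**Text as written.** Experimental post = L; control post = max(L, 42); one-month = L + 30 and three-month = L + 90 in both arms. The post to one-month intervals are:

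- experimental: (L + 30) − L = 30 days;
- control, L < 42: (L + 30) − 42 = L − 12 days.

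| L | Footnote date: post / one-month / three-month | Text, control: post / one-month / three-month | Text, control: post to one-month | Text, experimental: post to one-month |
|---|---|---|---|---|
| 12 | 42 / 72 / 132 | 42 / 42 / 102 | 0 | 30 |
| 21 | 42 / 72 / 132 | 42 / 51 / 111 | 9 | 30 |
| 28 | 42 / 72 / 132 | 42 / 58 / 118 | 16 | 30 |
| 35 | 42 / 72 / 132 | 42 / 65 / 125 | 23 | 30 |
| 42 | 42 / 72 / 132 | 42 / 72 / 132 | 30 | 30 |
| 49 | 49 / 79 / 139 | 49 / 79 / 139 | 30 | 30 |

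The two readings differ by 42 − L days at one and three months and agree from L = 42 on. Under the text, a control with L below 12 is due for the one-month visit before the post-intervention visit.

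**Time off therapy at the one-month visit.** By the text it is 30 days for everyone. By the footnote date, for L < 42, it is 72 − L: 51 days at L = 21, against 72 − 42 = 30 for an experimental patient who ends on day 42.

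**Experimental arm.** The plan calls for six visits over six weeks. If they are weekly and the first falls 1 to 7 days after baseline (an assumption), the sixth falls on day 1 + 35 = 36 to day 7 + 35 = 42. Dropping the floor then moves the experimental post-intervention visit by 0 to 6 days.

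**Windows, any L.**

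| Visit | Table | Text | Conflict? |
|---|---|---|---|
| Post, experimental | ± 7 business days | 7 business days, after only | Yes |
| Post, control | ± 7 business days | no width given | Text incomplete |
| One-month | ± 7 business days | 7 business days | Not clearly |
| Three-month | ± 7 business days | 7 days | Yes |

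Seven business days span 9 to 11 calendar days, ignoring holidays, so the three-month tolerances differ by 2 to 4 days.

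**The case against.** The strongest reply is that the footnote mark sits only on the post-intervention column. On that view the footnote does not govern the one- and three-month visits, and the text does not contradict it there. This is a fair reading of the table, but it does not rescue the schedule. The L − 12 interval follows from the text alone: the control post-intervention visit has the floor and the one-month visit does not.

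Some of the timing is sound. The control post-intervention anchor is the same in footnote and text. If experimental visits are weekly and prompt, the shift in that arm at treatment completion is at most 6 days, within the table's tolerance. The primary outcome, the Motor Skills score, is not collected at three months, so the three-month conflict reaches only the patient-reported form and adverse events. All of this stands and limits the point.

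A reader might go further and infer that the trial is biased in a known direction, or that the adverse event comparison is invalid. The documents support neither. They do not say how long usual care lasts, so the share of controls with L below 42 is unknown. The two readings push in opposite directions, and the recall period of the adverse events questionnaire is not given. Nor would mixed practice make the data uninterpretable: if actual visit dates are kept, they can be analysed by elapsed time.

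**Conclusion.** The point holds as an inconsistency that should be fixed. For a last therapy visit before day 42, the plan gives two dates for the one- and three-month assessments if the footnote defines post-intervention throughout the table, and two dates for the experimental post-intervention visit. The text taken alone gives early-finishing controls a shorter interval than the experimental arm and, at the extreme, an impossible order of visits. The window conflicts at post-intervention and three months apply to every patient.

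The effect on the primary outcome falls mainly on the one-month contrast. Confidence is high for the conflict in the text and for the nominal arithmetic. It does not extend to how often the case arises or to any bias between arms, because both depend on usual-care durations that the documents do not report.

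**What to change.** Reconcile the schedule table, its footnote and the three evaluation sections to one reference date and one window per visit, the same in both arms. State in the three-month section, as in the others, which event governs when usual care and the programme end on different days. This review does not say which reference date to choose.

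Record days since baseline and days since the last therapy visit at each assessment, and state that the mixed model uses actual time. Capture the date of each adverse event, so that unequal follow-up time can be examined alongside the planned comparison.

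The cost is protocol wording, scheduling logic, two derived time fields and, if not already collected, one date per adverse event. No extra visits or staff are needed. The downside is that no single reference date equalises both time since baseline and time since therapy ended. Whichever is chosen, the recorded times have to be used in the analysis.

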Hypothesis: Patients who receive the ADL-enhanced program plus usual rehabilitation therapy will show greater improvements in the Motor Skills scores of the Assessment of Motor and Process Skills (the primary outcome), Self-care items in the Outcome and Assessment Information Set (clinical outcome), and Activity Measure for Post-Acute Care Home Health Short Form (patient-reported outcome) at treatment completion and less decline at 1-month and 3-month follow-up than usual rehabilitation therapy.

Secondary Objectives.

Secondary objective 1: To estimate the preliminary effect of the ADL-enhanced program on improving physical functioning at treatment completion and one month after the completion.

Hypothesis 1: Patients who receive the ADL-enhanced program plus usual rehabilitation therapy will show greater improvements in the Box and Block Test (upper extremity physical function), Jebsen Hand Function Test (upper extremity physical function), Timed-Up-and-Go Test (lower extremity physical function), and Short Physical Performance Battery (lower extremity physical function) at treatment completion and less decline at one-month follow-up than usual rehabilitation therapy.

Secondary objective 2: To assess the completion, satisfaction, and adverse event rates of the ADL-enhanced program.

Hypothesis 2a: We hypothesize that the program completion and satisfaction rates will be greater than 75%.

Hypothesis 2b: Fewer patients who receive the ADL-enhanced program will have hospitalizations, emergency room visits, and falls than patients who receive usual rehabilitation therapy at 1-month and 3-month follow-up.

Background and Rationale

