Study design overview. This is a single-blinded, pilot randomized controlled trial of 48 Medicare patients referred to HHC for skilled rehabilitation services. Twenty-four patients will be randomly assigned to the treatment-as-usual arm and receive usual rehabilitation services. The other 24 patients in the experimental arm will receive the ADL-enhanced program in six OT visits as well as usual rehabilitation services.

Selection and Enrollment of Participants

Participants will be recruited from partnered home health agencies

Inclusion criteria. Patients are eligible to the study if they are:

- (1) \geq 65 years of age,
- (2) Medicare beneficiaries,
- (3) referred for skilled rehabilitation services; and
- (4) diagnosed with three or more comorbidities.

Exclusion criteria. Patients are ineligible if they have contraindications for moderate-intensity exercise, which include:

- acute fractures with surgical or weight-bearing restrictions,
- elective joint replacement surgery,
- lower extremity amputation,
- active treatment for cancer diagnosis,
- on-going dialysis treatment,
- acute cardiac surgery,
- acute stroke or a major neurologic disorder limiting motor movements,
- terminal stage of congestive heart failure,
- a referral to hospice care, or
- severe cognitive deficits limiting verbal communication.

Enrollment Procedures.

Screening procedure. The home health care team will obtain verbal permission from new patients to allow the research coordinator to contact and screen the new patients via phone. The coordinator will record the screening results (fail or pass) on a screening log. The coordinator will call the eligible patient, verify the eligibility, and introduce the study.

Consent procedure. The coordinator will then conduct a recruitment home visit to the eligible patient and obtain consent at the end of the visit. If the patient does not provide consent during the recurrent home visit but decides to participate in the study afterwards, a study outcome assessor will obtain consent at the beginning of the baseline assessment visit. Reasons of rejection will be recorded.

Patients who are eligible and agree to participate will be referred to the study outcome assessor, who will schedule the patient within 48 hours to obtain the consent, if not yet obtained by the research coordinator, and complete the baseline assessments (ADL and physical functioning assessments) at the participant's home. The assessor will be blinded to group assignments.

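### The Day 90 call may be made by the coordinator who knows the allocation, so the 3-month AM-PAC and adverse-event data may be collected unblinded in a trial described as single-blinded

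*Combined protocol and SAP*

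**What the plan says.** The Study design overview describes the trial so: "This is a single-blinded, pilot randomized controlled trial". The enrolment text makes the outcome assessor the blinded party.

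The coordinator's role is set out in two places:

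- Randomization: "The on-site research coordinator will open one envelope after a patient has completed the baseline assessments". If the patient is in the ADL-enhanced arm, the coordinator then alerts the study therapist.
- Post-intervention evaluation: "The satisfaction survey will be given to the patient in the experimental group". The coordinator does this by phone after the last study visit.

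The post-intervention and one-month evaluations both include the AM-PAC and the adverse-event questionnaire, and both are given to the blinded assessor. The one-month section reads "The one-month follow-up evaluation conducted by the blinded outcome assessor", and both sections add: "Patients will be instructed not to discuss their therapy content with the blinded outcome assessor and vice versa".

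The Day 90 section repeats those two instruments but assigns them differently: "The final evaluation will occur over the phone by the research assistant or coordinator within seven days three months after the completion". It mentions neither blinding nor the instruction about discussing therapy.

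Two stated hypotheses use the 3-month data. The primary hypothesis expects "less decline at 1-month and 3-month follow-up than usual rehabilitation therapy". Hypothesis 2b expects that "Fewer patients who receive the ADL-enhanced program will have hospitalizations, emergency room visits, and falls", compared with usual therapy, at one and three months.

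**The concern.** The plan uses a blinded assessor for these two instruments at both earlier post-randomization visits, then drops that protection at the last one without giving a reason. One of the two roles allowed to make the Day 90 call cannot be blind to the arm, and nothing requires the other to be.

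In the Schedule of Evaluations, the AM-PAC is the only ADL measure at three months. All the 3-month between-arm evidence on ADL and adverse events therefore comes from this call. A caller who knows the arm can influence how AM-PAC items are put, probed and recorded, and how hard falls are asked about. Hospitalizations and emergency room visits are discrete events and less exposed.

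The person asking also changes between the one-month and 3-month AM-PAC, which is the interval over which decline is to be compared. A change common to both arms would not bias the contrast; a change to a caller who treats the arms differently would.

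**Working it through.** **Roles by evaluation**

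| Evaluation | Who collects AM-PAC and adverse events | Blinding stated | Instruction not to discuss therapy |
|---|---|---|---|
| Post-intervention | Outcome assessor | Yes | Yes |
| One month | Outcome assessor | Yes | Yes |
| Day 90 (phone) | Research assistant or coordinator | No | No |

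**What the coordinator knows.** The coordinator opens the envelope, acts on its content by alerting the therapist, and later phones only the experimental arm for the satisfaction survey. Each of these tasks requires or reveals knowledge of the arm. The documents do not say that a different coordinator makes the Day 90 call.

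**Illustration of size for the AM-PAC.** The documents give no bias, SD, alpha or correlation, so the plan has no figure to reproduce. Inputs:

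- 24 per arm, from the Study design overview, with full retention assumed.
- Two-sided 5% test (assumed).
- Correlation of 0.6 between time points (assumed).
- Between-arm bias *b* of 0 to 0.3 SD, same direction on every call (assumed).

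With no true effect, the chance of a significant result is P(|Z + *b*/SE| > 1.96), where Z is standard normal. The standard errors, in SD units, are:

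- 3-month score, unadjusted: √(2/24) = 0.2887
- 3-month score, baseline-adjusted: 0.2887 × √(1 − 0.6²) = 0.2309
- Change from one month to three months: √((2/24) × 2 × (1 − 0.6)) = 0.2582. The one-month score is taken as unbiased, so all of *b* passes into the change.

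| Bias *b* (SD) | Unadjusted | Baseline-adjusted | One- to 3-month change |
|---|---|---|---|
| 0 | 5.0% | 5.0% | 5.0% |
| 0.1 | 6.4% | 7.2% | 6.7% |
| 0.2 | 10.7% | 13.9% | 12.1% |
| 0.3 | 18.0% | 25.5% | 21.3% |

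For example, with *b* = 0.3 unadjusted, *b*/SE = 0.3/0.2887 = 1.04, which gives 18.0%. If only half the calls carry the 0.3 SD bias, the mean bias is 0.15 SD and the rate is about 8% unadjusted or 10% baseline-adjusted.

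No corresponding calculation was made for the Fisher's exact comparison of adverse events, because the documents give no event rate.

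**The case against.** The strongest case against giving this much weight has five parts.

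1. **The text permits unblinded calls but does not require them.** The research assistant is named first, and that the Day 90 coordinator is the person who opened the envelope is an inference, though a reasonable one. This stands, and it is why the point is worded as a possibility.
2. **Blinding is attached to the outcome assessor, and the plan openly gives Day 90 to other staff.** There is no flat contradiction of the single-blind label. That is fair, but the label carries no exception for Day 90, and a reader would take the 3-month results as covered by it.
3. **The consequence is limited.** The Assessment of Motor and Process Skills, which is the primary outcome, is not measured at Day 90. The AM-PAC is patient-reported and no blinding of patients is described, so a blinded caller removes only the interviewer's influence. The analysis text names three time points and not the 3-month one, so it is unclear whether a 3-month AM-PAC contrast will be tested. All of this stands. It limits the severity, but the objectives still promise 3-month comparisons, and the interviewer's influence is the part that is easy to avoid.
4. **The figures rest on assumed inputs.** They do. In a pilot meant to estimate effects, the bias itself matters more than the false-positive rate. The conclusion rests on the assignment of roles and does not need these figures.
5. **Labelling every 3-month result as unblinded would be wrong where an unaware assistant made the call.** This is correct, and the fallback below allows for it.

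**Conclusion.** The concern holds as a possibility that the plan leaves open. As written, a person who knows the allocation may collect all the 3-month AM-PAC and adverse-event data, without the two safeguards applied to the same instruments at the earlier post-randomization visits. This should be corrected, but it does not threaten the primary outcome. Nor does it cover the OASIS self-care scores, which the coordinator takes from the chart and which are a separate matter.

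The size of any bias cannot be derived from the documents. Under the stated assumptions, a bias of 0.1 SD or less matters little (at most about 7% against a nominal 5%). At 0.3 SD on every call the rate is 18% to 25%, depending on the analysis. Among the adverse events, falls are the most exposed.

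**What to change.** In the Final evaluation section, remove the coordinator as a permitted caller. Name either the existing blinded outcome assessor or a research assistant who has no access to allocation. Removing the coordinator alone is not enough unless the assistant is also kept unaware of the arm. Add a fixed call script and the instruction about not discussing therapy that the earlier visits already use.

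If calls have already been made, record who made each one. Report the 3-month AM-PAC and adverse-event results as not collected under blinding where the coordinator called, and as blinding not assured where an assistant called and their awareness of the arm cannot be established.

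The cost is a small wording change and at most 48 short phone calls (24 + 24 patients). The downside is some assessor time. The documents do not describe staffing, so the assessor's availability is an assumption. If no blinded caller can be found, the reporting fallback needs no extra calls.
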